For assessment of passive glenohumeral internal rotation, participants laid supine with 90° of shoulder abduction in the frontal plane and the elbow flexed at 90°. ¹¹ The examiner stabilized the scapula with one hand by applying mild pressure to its anterior aspect (coracoid process), while applying with the other hand a passive movement of shoulder internal rotation to its maximal point. An assistant read the measurement placing the goniometer with the stationary arm parallel to the floor and the mobile arm in alignment with the forearm starting at the olecranon.³⁹ The same starting posture and goniometer positioning will be used for measuring passive glenohumeral external rotation.

Experimental conditions (independent variables)

There are two independent variables in the research design: treatment condition and time (pre-, post-application). Treatment condition has three levels, which include the AP shoulder mobilization, a manual contact and a no-contact condition.⁴⁷ These experimental conditions will be administered in random order in three separated sessions to all participants, with each session separated by 48 h in order to control for carry-over effects.³⁵ The treatment allocation sequence will be randomized using sealed envelopes and concealed from the investigator who took the outcome measurements. An experienced physiotherapist with a Master degree on manual therapy and more than 10 years of working experience will apply all conditions. This physiotherapist will be blinded to the results of the measurements and questionnaires used as outcome measures.

All conditions will be applied for a total of 10 min, comprising three sets of 3 min, alternating with 30-s rests. Verbal instructions and positioning will be strictly standardized during all the sessions.

Treatment condition

The treatment condition consist on the application of a passive rhythmic AP mobilization to the glenohumeral joint of the affected shoulder. In particular, a Grade III AP glide to the humeral head with the arm positioned in 90° of glenohumeral abduction and full internal rotation was used.⁴⁷ The posterior gliding force to the humeral head was applied maintaining the glide at right angles to the plane of movement and at a frequency of 2 Hz which will be controlled by means of a metronome. The arm will be returned to its original position between each set.

Manual contact condition

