During the manual contact condition the therapist positione the patient in a mid-range position of glenohumeral abduction and internal rotation and apply the hands to the same contact point as in the treatment condition. However, a simulated posterior glide will be performed but with minimal pressure actually applied.⁴⁷ The number of repetitions and sets were as per the treatment condition.

No-contact condition

During the no-contact condition, the subject remain in the initial starting position thorough the entire session but there are no manual contact between the therapist and the participant.⁴⁷ The total treatment time will be the same as per the other conditions.

Procedure

At the first session and after recording demographic data, the NRPS and DASH will be administered followed by PPT, ROM and muscle strength measurements in a standardized order. Subjects then will received the assigned intervention for that session and, immediately afterwards, all outcome measures will be reassessed following the same order as before. The only exception was the DASH, which will be assessed before and 24 hours after each experimental condition. This procedure will be repeated for all the three test sessions.

An investigator, will blinded to the allocated intervention, performed all the outcome measures before and immediately after the application of the three experimental conditions. Discussion between researchers and subjects will be minimized during treatment in order to facilitate subject blinding and reduce potential interactions. No feedback will be given on performance until after the final session. The extent of subject blinding will be assessed through a short, self-administered, post-experiment questionnaire, where participants will be asked to indicate whether they have experienced a physiotherapy treatment in any of the sessions and, if so, in which session.³⁵

Statistical analysis

Data will be analysed using SPSS 22 for Windows. Statistical significance will be set at $p < 0.05$.

Two independent variables will be incorporated into the research design: treatment (AP mobilization, manual contact, no-contact) and time (pre- and post-intervention). Five dependent variables will be considered including PPT, muscle strength, NRPS, DASH (disability/symptom section) and ROM.

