Descriptive statistics will be calculated to describe baseline data. A two-way analysis of variance (ANOVA) through a General Linear Model and appropriate post-hoc tests of simple effects will be used to evaluate hypothesis that AP mobilization produced more changes than manual contact and no-contact conditions from pre- to post-intervention ($P=0.05$). The between subject factor will be treatment condition (AP mobilization, manual contact, no-contact) with time (pre and post-intervention) as within subject factors.

Sphericity will be confirmed by means of Mauchly's test. Bonferroni test will be used for multiple comparisons and the effect size will be estimated using Eta square (η^2) when significant. An effect size of 0.01 will be considered small, 0.06 medium and 0.14 large.⁷

REFERENCES

7. Cohen J. *Statistical Power Analysis for the Behavioral Sciences.* New York, NY: Routledge Academic, 1988.

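### The 0.01/0.06/0.14 labels are applied to an unnamed eta-squared, and only when significant, so the label depends heavily on sample size and on the denominator chosen

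*Protocol*

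**What the plan says.** Under Experimental conditions, the protocol describes a crossover: "These experimental conditions will be administered in random order in three separated sessions to all participants". Each participant therefore contributes a pre and a post value under AP mobilization, manual contact and no contact.

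The Statistical analysis section plans a two-way ANOVA at the 5% level with the factors "treatment (AP mobilization, manual contact, no-contact) and time (pre- and post-intervention". It assigns the roles as follows: "The between subject factor will be treatment condition (AP mobilization, manual contact, no-contact) with time (pre and post-intervention) as within subject factors". On effect size it says that "the effect size will be estimated using Eta square (η^2) when significant", and then "An effect size of 0.01 will be considered small, 0.06 medium and 0.14 large".

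The section does not say whether eta-squared is partial, classical or generalized. It names no other measure of effect size. The protocol states no sample size.

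**The concern.** Partial eta-squared divides the effect's sum of squares by that effect plus its own error term. Classical eta-squared divides it by the total sum of squares, which here includes the stable differences between athletes. With repeated measures on the same people the two can be far apart, so fixed cut-offs can give different labels to one dataset.

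Reporting eta-squared only after a significant test adds a second problem. Significance puts a floor under partial eta-squared, and the floor depends on the degrees of freedom. In a small trial the floor can lie above a cut-off, and the labels below it can then never appear.

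This is the protocol's only rule for saying how big an effect is. A result called large might reflect little more than p<0.05 in a small sample, yet be read as a clinically important change in pain threshold, strength or range of motion.

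**Working it through.** The plan has no figure of its own to reproduce: it states no sample size, power or expected effect.

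**Inputs from the protocol.** Three conditions by two times, so the interaction has 2 numerator df; alpha 0.05; cut-offs 0.01, 0.06 and 0.14; eta-squared reported only when significant.

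**Assumptions.** The sample size n is varied. The within-person correlation (ICC) is varied from 0 to 0.95, with compound symmetry.

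**Step 1: floor of partial eta-squared.** With error df *d*, the smallest significant value for treatment-by-time is 2F/(2F + d), where F is the 95th percentile of F(2, d).

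*Both factors within person, as the crossover implies: d = 2(n−1).*

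| n | d | F | Smallest significant partial value |
|---|---|---|---|
| 15 | 28 | 3.340 | 0.193 |
| 20 | 38 | 3.245 | 0.146 |
| 21 | 40 | 3.232 | 0.139 |
| 30 | 58 | 3.156 | 0.098 |
| 49 | 96 | 3.091 | 0.0605 |
| 50 | 98 | 3.089 | 0.059 |

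For n=20: 2×3.245/(2×3.245 + 38) = 6.490/44.490 = 0.146. The floor stays at or above 0.14 up to n=20 and at or above 0.06 up to n=49. At n=20 a sphericity correction raises it further, to 0.162 at epsilon 0.75 and 0.187 at epsilon 0.5.

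*Treatment between subjects, as written, with the 3n session records treated as separate subjects: d = 3n−3.*

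| n | d | F | Smallest significant partial value |
|---|---|---|---|
| 14 | 39 | 3.238 | 0.142 |
| 15 | 42 | 3.220 | 0.133 |
| 20 | 57 | 3.159 | 0.100 |
| 33 | 96 | 3.091 | 0.0605 |
| 34 | 99 | 3.088 | 0.059 |

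The limits become n=14 for 0.14 and n=33 for 0.06.

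**Step 2: classical eta-squared for the same just-significant within-person effect, n=20.** Scale the total variance of one observation to 1 and write r for the ICC.

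- Interaction SS = 2×3.245×(1−r) = 6.490(1−r).
- Total SS: the interaction; the other within-person terms, 95 error df (5×19) plus 3 df for the two main effects taken as null, each worth (1−r); and the between-person SS, 19×[(1−r) + 6r].
- Total SS = (1−r)(6.490 + 95 + 3 + 19) + 114r = 123.490(1−r) + 114r.

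At r=0.5: 3.245/(61.745 + 57) = 3.245/118.745 = 0.027.

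| ICC | Partial | Classical |
|---|---|---|
| 0 | 0.146 | 0.053 |
| 0.5 | 0.146 | 0.027 |
| 0.7 | 0.146 | 0.017 |
| 0.8 | 0.146 | 0.011 |
| 0.9 | 0.146 | 0.0056 |
| 0.95 | 0.146 | 0.0028 |

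Setting the ratio to 0.01 gives 6.490(1−r) = 1.235(1−r) + 1.14r, so r = 5.255/6.395 = 0.82. Below that correlation the classical value at this boundary reads small; above it, it falls under the lowest cut-off. The partial value stays just above 0.14 throughout.

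**The case against.** The strongest reply is that the labels are descriptive. They are applied after the test and alter no p-value, and the choice of eta-squared is often left to an analysis plan. That much stands. But the protocol itself fixes the cut-offs and the reporting condition, and nothing it contains says which statistic they grade.

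Several stronger readings are tempting, and the documents do not support them:

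- **Every significant result in this trial will be called large.** No sample size is stated, and the n=20 limit needs treatment to be analysed within person. Under the between-subject model as written, the floor at n=20 is 0.100. In simulations at that n, about 37% to 73% of significant interactions had a partial value below 0.14.
- **Significance and n alone fix the label.** They set only a floor. Partial eta-squared still rises with F, and so with the change relative to its error.
- **Classical eta-squared would call a real effect trivial.** A value below 0.01 for the just-significant effect at n=20 needs a within-person correlation of about 0.8 or more. At lower values it reads small.
- **The cut-offs were made for independent groups, or the software settles the matter by printing the partial form.** The protocol says only "Data will be analysed using SPSS 22 for Windows", and the cited source for the cut-offs is not at hand. The point rests on neither.

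It can also be said that the planned post-hoc tests, with "Bonferroni test will be used for multiple comparisons", compare means in original units. They do, but the protocol does not make those differences, with intervals, its measure of effect size.

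**Conclusion.** The point holds in limited form. The grading rule is fixed, the statistic it grades is not named, and grading happens only after significance. For partial eta-squared of treatment-by-time, neither small nor medium can occur up to n=20, and small cannot occur up to n=49, if both factors are within person. The limits are n=14 and n=33 under the model as written. At n=20 a just-significant within-person effect is 0.146 in partial form and, in classical form, 0.053 to 0.0028 over assumed correlations of 0 to 0.95. The first is large by the rule; the second is small or below.

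The size of the problem depends on n and on the within-person correlation, and the protocol gives neither. From n=50 (n=34 under the written model) all three labels can occur for partial eta-squared, although the two forms can still disagree. The harm is to interpretation: inference is untouched, but the label says little about how far pain, strength or motion moved. The change should be made, and it need not hold up the analysis.

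**What to change.** Replace the two effect-size statements in the Statistical analysis section. Make the effect measure the difference in pre-post change, AP mobilization minus manual contact and AP mobilization minus no contact. Give it in each outcome's original units with a 95% CI from the within-person analysis, and report it for every outcome whether or not it is significant.

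If eta-squared is kept, name its type and do not grade it with the 0.01/0.06/0.14 cut-offs. In the same edit, reconcile the sentence that makes treatment a between-subject factor with the crossover design, because the intervals depend on it.

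The cost is a few sentences of wording and no new data. The downside is that results may look less impressive than a large label would make them.
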